² Screening laboratory tests include: ALT, AST, creatinine (and calculate an estimated glomerular filtration rate (eGFR) the formula used is determined by the sites, but should be consistent throughout the study), and urine or serum pregnancy test for females of child-bearing potential. Laboratory tests performed as part of routine clinical care in the 48 hours prior to enrollment will be accepted for determination of eligibility.

³ Baseline assessments should be performed prior to first infusion. Laboratory tests performed as part of routine clinical care in the 24 hours prior to first dose will be accepted for the baseline safety laboratory tests. Baseline may be the same as the screening laboratory tests if obtained in the 24 hours prior to first dose.

⁴ Safety laboratory tests include WBC with differential, hemoglobin, platelets, creatinine, total bilirubin, ALT, AST, and INR.

⁵ Any laboratory tests performed as part of routine clinical care within the specified visit window can be used for safety laboratory testing. ⁶ In-person visits are preferred but recognizing quarantine and other factors may limit the subject's ability to return to the site for the visit. In this case, the visit may be performed by phone.

- If still hospitalized at Day 15 and 29 or returns for an in-person visit: assess adverse events, collect clinical data, vital signs, safety laboratory tests, and research laboratory samples (OP swab and blood) as able.
- If phone call only on Days 15 and 29 and all Day 22 and Day 60 visits: assess adverse events, clinical status (ordinal scale), readmission to a hospital, and mortality only.

⁷ Oropharyngeal swabs are preferred, but if these are not obtainable, saliva or nasopharyngeal or nasal swabs may be substituted. ⁸ Pre-dose serum sample collections for PK and immunogenicity.

⁹ To include markers of inflammation and coagulation: CRP, ferritin, fibrinogen, d-dimer.

¹⁰ Day 8, 22 and 60 visits performed by phone call or home visit if discharged from the site hospital: assess adverse events, clinical status (ordinal scale), readmission to a hospital, and mortality only.

¹¹ Only collected at selected sites capable of processing.

¹² Steroids and other concomitant therapies intended as specific treatment of COVID-19, as well as all biologics, will be assessed from 7 days prior to enrollment to Day 29. All other concomitant medications will be assessed from 7 days prior to enrollment to Day 15 or upon discharge, whichever comes first.

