6.5 Concomitant Therapy

6.5.1 Permitted Concomitant Therapy and Procedures

For patients that are eligible for the study, other therapy received prior to enrollment with any other experimental treatment or off-label use of marketed medications that are intended as specific treatment for COVID-19 or the SARS-CoV-2 infection (i.e., post-exposure prophylaxis [PEP]) are permitted but must be discontinued on enrollment. There is no waiting period between discontinuation of these treatments and administration of study products. However, these prior treatments and their end date should be documented on the concomitant medication form in the EDC system.

Steroids for the treatment of COVID-19 may be used per the local institution's written standard of care (i.e., not just an individual clinician decision) or NIH COVID-19 Treatment Guidelines (https://www.covid19treatmentguidelines.nih.gov/). NIH COVID-19 Treatment Guidelines provide current evidence-based information about the optimal management of COVID-19. NIH COVID-19 Treatment Guidelines were updated on June 25, 2020 to include a Grade AI recommendation for using dexamethasone (6 mg per day for up to 10 days) in patients with COVID-19 who are mechanically ventilated and a Grade B1 recommendation for patients with COVID-19 who require supplemental oxygen but who are not mechanically ventilated based on preliminary data from the RECOVERY trial. The NIH Guidelines also recommend against using dexamethasone in COVID-19 patients who do not require supplemental oxygen.

Steroid regimens for other standard indications including asthma exacerbation, ARDS, COPD, laryngeal edema, adrenal insufficiency, shock, etc. are allowable up to a maximum of prednisone 60 mg daily or equivalent. All steroid use regardless of indication until Day 29 will be recorded in the EDC system.

Subjects who are taking another antiviral for a concurrent infection (e.g. oseltamivir for an influenza virus) or another existing medical condition (e.g. hydroxychloroquine for lupus) may

continue with the treatment. Note that these treatments may be thought of as an off-label medication for COVID-19, however, because they were being used prior to study enrollment for another indication, they are allowable.

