- Values of WBC with differential, hemoglobin, platelets, creatinine, eGFR, total bilirubin, ALT, AST, and INR on Study Days 1, 3, 5, 8, and 11 (while hospitalized); and Study Days 15 and 29 (if attends in-person visit or still hospitalized).

Exploratory Endpoints

The exploratory endpoints are:

- Whether a subject used concomitant COVID-19 treatments (e.g., steroids) post-baseline up to and including Study Day 29.

Details for the exploratory endpoints listed below are not provided in this master SAP will be provided in a separate SAP addendum and reported in a separate CSR addendum.

- Whether a subject has detectable SARS-CoV-2 according to polymerase chain reaction (PCR) in saliva from oropharyngeal (OP) swab (or best technology) on Study Day 1; Study Days 3, 5, 8, and 11 (while hospitalized); and Study Days 15, and 29 (if subject attends in-person visits or is still hospitalized);
- Quantitative polymerase chain reaction (PCR) for SARS-CoV-2 in saliva from OP swab on Study Days 1, 3, 5, 8, and 11 (while hospitalized); and Study Days 15 and 29 (if subject attends in-person visit or is still hospitalized);
- Whether a subject has detectable SARS-CoV-2 in blood at Study Days 1, 3, 5, 8, and 11 (while hospitalized);
- Quantitative PCR for SARS-CoV-2 in blood on Study Days 1, 3, 5, 8, and 11 (while hospitalized);
- Proteomic analysis of plasma cytokines and markers of inflammation;
- Transcription, epigenetic, and molecular profiles of mRNA in peripheral blood mononuclear cells (PBMC);
- Phenotypic and responsiveness markers in PBMC.

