AE Stop Date	MM	UNK	YYYY	IMPUTE with last day of MM/YYYY or last assessment day if never discharged or last assessment month/year is the same as MM/YYYY
CM Dates				
CM Start Date	UNK	UNK	UNK	IMPUTE with FIRST_DOSE date; Default = make CM start date/time a CM with earliest possible date; Impute with randomization date if not treated, or informed consent date for other subjects. In cases with imputed start date after stop date, impute start date as stop date.
CM Start Date	UNK	UNK	YYYY	IMPUTE with 01/01/YYYY, or FIRST_DOSE date (or randomization date if not treated) if in same year; if first dose is later in that year, start date= 01/01/YYYY. In cases with imputed start date after CM stop date, impute start date as stop date.
CM Start Date	MM	UNK	YYYY	IMPUTE with MM/01/YYYY, or FIRST_DOSE (or randomization date if not treated) if it is in same month/year. In case that imputed start date is after CM stop date, impute start date with stop date.
CM Stop Date	UNK	UNK	UNK	IMPUTE with discharge date, or last assessment date if never discharged or last assessment date is after discharge date
CM Stop Date	UNK	UNK	YYYY	If discharge date or last assessment date is YYYY, IMPUTE with discharge date if discharged, or last assessment date if never discharged. If discharge date or last assessment date is YYYY+1 then IMPUTE AE Stop date as 12/31/YYYY.
CM Stop Date	MM	UNK	YYYY	IMPUTE with last day of MM/YYYY or last assessment day if never discharged or last assessment month/year is the same as MM/YYYY
MH Dates				
MH Start Date	UNK	UNK	UNK	IMPUTE with FIRST_DOSE date; Default = make MH start date/time a MH with earliest possible date. Impute with randomization date if not treated, or informed consent date for other subjects. In case that imputed start date is after stop date, impute start date with stop date.
MH Start Date	UNK	UNK	YYYY	IMPUTE with 01/01/YYYY
MH Start Date	MM	UNK	YYYY	IMPUTE with MM/01/YYYY
MH Stop Date	UNK	UNK	UNK	IMPUTE with discharge date, or last assessment date if never discharged or last assessment date is after discharge date
MH Stop Date	UNK	UNK	YYYY	IMPUTE with 12/31/YYYY
MH Stop Date	MM	UNK	YYYY	IMPUTE with last day of MM/YYYY

Listings should not present imputed dates; listings should present partial dates or “.” if date is entirely missing.

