9.1.2. Prior and Concomitant Medications

Concomitant medications will be coded to the Anatomical Therapeutic Classification using the WHODrug Dictionary. The use of prior and concomitant medications taken during the study will be recorded on the CRFs.

Prior medications are defined as any medications begun and stopped before a subject took the first dose of study product. If a partial stop date is entered, the month and year (if day is missing) or year (if day and month are missing) of the stop date are prior to the first dosing date will be considered prior (See [Table 8](#)).

Concomitant medications are defined as medications taken while a subject took study product. Therefore, any medications started prior to or during the first dosing date of study product and continued after the first dosing date or started after the first dosing date will be considered concomitant medications. If a partial start date is entered, any medication with the month and year (if day is missing) or year (if day and month are missing) after the date of first study product administration will be included in the concomitant medication summary. Medications with completely missing start and stop dates will be included in the concomitant medication summary ([Table 8](#)).

Prior and concomitant medications reported on the concomitant medication form will be summarized separately WHO Drug Level 1 and 2 Codes, actual baseline ordinal score, and treatment group using the number and percentage of subjects for each treatment, actual baseline ordinal score, and overall ([Table 84](#), [Table 85](#)). Concomitant COVID-19 treatments are reported in [Table 86](#) while steroids used for indications other than COVID-19 are reported in [Table 87](#). A subject reporting the same medication more than once will be counted only once when calculating the number and percentage of subjects who received that medication. The summary will be ordered alphabetically by WHO Drug level 1 code then by WHO Drug level 2 code in order of descending overall frequency within each WHO Drug level code. For drugs with the same frequency, sorting will be done alphabetically.

Summaries of prior and concomitant medications will be based on the Safety population and individual subject listing of all prior and concomitant medications including those reported on the SAE form is provided in [Listing 9](#), [Listing 10](#) for steroids, and [Listing 11](#) for other medication of interest.

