Concomitant COVID-19 Treatments are defined as medications that started before dose 1 of study product and continued throughout the study or those started after a subject took study product.

SD=Standard Deviation. Min=Minimum. Max=Maximum.

N=Number of subjects in the Safety population.

n=Number of subjects reporting at least one of the concomitant COVID-19 treatments. Refer to Section 6.4 for a list of COVID-19 treatments of interest.

^a Study day onset is defined as the start day of the concomitant medication.

Table 87: Summary of Steroid Usage for Indications Other than COVID-19 by Treatment of Indication — Safety Population

Type	Summary Measure	Treatment A (N=X)						Treatment B (N=X)					
		n	Mean	SD	Median	Min	Max	n	Mean	SD	Median	Min	Max
[COVID-19 Treatment 1]	Number of Subjects	x	-	-	-	-		x	-	-	-	-	-
	Study Day Onset ^a	x	x.x	x.xx	x.x	x	x	x	x.x	x.xx	x.x	x	x
	Duration (days)	x	x.x	x.xx	x.x	x	x	x	x.x	x.xx	x.x	x	x

Concomitant Steroid Treatments are defined as steroids for indications other than COVID-19 that started before dose 1 of study product and continued throughout the study or those started after a subject took study product.
SD=Standard Deviation. Min=Minimum. Max=Maximum.
N=Number of subjects in the Safety population.
n=Number of subjects reporting steroid usage for indications other than COVID-19. Refer to Section 6.4 for a list of steroids of interest.
^a Study day onset is defined as the start day of the concomitant medication.

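### SAP Tables 86 and 87 leave out short treatment courses already running at first dose, and Table 8 can place an unknown stop date near Day 60 although these drugs are collected only to Day 29

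*SAP*

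**What the plan says.** The exploratory endpoint in SAP 3.2 is "Whether a subject used concomitant COVID-19 treatments (e.g., steroids) post-baseline up to and including Study Day 29". SAP 8.3 adds onset and duration by arm. The shells for these summaries are Tables 86 and 87 in SAP Appendix 1. (For the first, 8.3 cites Table 78, which is a hemoglobin table; Table 86 is evidently meant.)

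- **Definition.** The Table 86 footnote defines the treatments to be counted as "medications that started before dose 1 of study product and continued throughout the study or those started after a subject took study product". Table 87 uses the same rule but covers only steroids for indications other than COVID-19. SAP 9.1.2, which names both tables among its outputs, instead counts "any medications started prior to or during the first dosing date of study product and continued after the first dosing date", plus drugs started later. The implementation note for Table 85 agrees with 9.1.2.
- **Stop dates.** For a concomitant-medication stop date with day, month and year all unknown, Table 8 (SAP 6.6) says "IMPUTE with discharge date, or last assessment date if never discharged or last assessment date is after discharge date". SAP 8.3 refers drugs ongoing at study end to the same table.
- **Collection.** In Protocol 1.2, footnote 12 reads "Steroids and other concomitant therapies intended as specific treatment of COVID-19, as well as all biologics, will be assessed from 7 days prior to enrollment", with the period ending at Day 29. The medication-review row is marked at Days 8, 15, 22 and 29, and Protocol 6.5.1 requires all steroid use to be recorded until Day 29. Yet footnotes 6 and 10 tell sites, for telephone contacts, to "assess adverse events, clinical status (ordinal scale), readmission to a hospital, and mortality only".

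**The concern.** Exploratory objective 3 compares use of key COVID-19 treatments between arms after baseline. Patients enter on oxygen or ventilation, and the SAP makes baseline steroid use a covariate in its primary model, so it expects some to be on steroids at dosing. Tables 86 and 87 are the only by-arm tables with onset and duration. If their footnotes are programmed literally, a short course that straddles the first dose disappears from them. If Table 8 is programmed literally, a course with no known stop date is extended about a month beyond the period in which these drugs are collected. The counts of courses running at dosing, the onset days and the durations would then be wrong, even though each program followed the plan.

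**Working it through.** The plan gives no figure for these summaries, so there is none to reproduce. The check is day arithmetic.

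**Inputs**
- No Day 0; Study Day 1 is the first-dose day (SAP 3.3.1).
- Duration is the number of days between onset and end (SAP 8.3).
- Course length: Protocol 6.5.1 cites "dexamethasone (6 mg per day for up to 10 days"; only the length is used here.
- End of collection: Day 29. Last visit: Day 60 ± 3, so Days 57 to 63.
- Assumed, because the documents give no value: start days, and 5% to 30% of courses with a fully unknown stop date.

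**1. Pre-dose courses.** A course of L days begun on Day -s ends on Day L - s.
- L = 10: begun on Day -7, it ends on Day 10 - 7 = 3; begun on Day -1, on Day 10 - 1 = 9. Each start day from -7 to -1 gives a course that continues past dosing, so 9.1.2 and Table 85 count it.
- To last until Day 29, a course begun on Day -1 needs 29 + 1 = 30 days; to last until Day 57 it needs 57 + 1 = 58 days. Whichever day is taken as the end of the study, no 10-day course qualifies.
- With a known stop date, every such course is therefore left out of Tables 86 and 87.

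**2. Unknown stop date.** Take a 10-day course from Day 2 to Day 11 in a discharged completer.
- True duration: 11 - 2 = 9 days.
- Imputed: 57 - 2 = 55, 60 - 2 = 58, or 63 - 2 = 61 days.
- Mean duration when a fraction f of stops is unknown (last assessment on Day 60): 9(1 - f) + 58f = 9 + 49f. With the stop capped at Day 29 the imputed duration is 29 - 2 = 27, and the mean is 9 + 18f.

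| f (assumed) | Mean, Table 8 as written | Mean, cap at Day 29 |
|---|---|---|
| 0.05 | 11.45 | 9.9 |
| 0.10 | 13.9 | 10.8 |
| 0.20 | 18.8 | 12.6 |
| 0.30 | 23.7 | 14.4 |

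- A gap between arms of 5 percentage points in unknown stops would by itself create a difference of 0.05 × 49 = 2.45 days in mean duration; 10 points, 4.9 days.

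**3. Interaction.** Take two subjects with the same 10-day course begun on Day -1. In one the stop is documented as Day 9, and the course is dropped. In the other the stop is unknown and is imputed to Day 60; the course now appears to last the whole study and can be kept, with a duration of 1 + 59 = 60 days. The poorer record is retained and the better one discarded. In addition, SAP 8.3 sets onset to Day 60 in means and medians for subjects with no treatment applied. A subject whose only course was dropped could be given that onset if the footnote is applied literally.

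**The case against.** The strongest reply is that this is loose shell wording against a clear rule in the body of the SAP, for exploratory summaries with no test or decision attached. Much of that stands. Section 9.1.2 is right and points to these tables. The endpoint is yes/no, so a wrong stop date does not change it for a drug started after dosing, and Table 86 does count such drugs. Some information survives elsewhere: Table 14 shows steroid use by arm, Table 85 counts courses continuing past first dose by drug class, and Listings 9 to 11 show individual records. None of these summarises onset or duration by arm.

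A reader might also infer more than the documents support:

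- **That phone visits do not ask about drugs.** Footnotes 6 and 10 read that way, but the medication-review row, footnote 12 and Protocol 6.5.1 say the opposite, and recording details are left to a manual not provided here. What is shown is a contradiction, with a risk of under-capture after discharge.
- **That every incomplete stop date moves to about Day 60.** Where only the year is known, Table 8 generally uses the discharge date for a discharged subject. Where the month is known, it uses month end or the last assessment, which in most cases keeps the date within that month. Subjects who die or leave early get an earlier date. Protocol 6.5.1 also excludes corticosteroids and biologics from its record-once shortcut, which should limit missing dates in hospital.
- **That the arm discharged earlier will appear treated longer.** A fully unknown stop goes to the last assessment both in subjects never discharged and in those assessed after discharge. A direction would need discharge, follow-up or date completeness to differ by arm.

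**Conclusion.** The point holds in limited form. The Table 86 and 87 footnotes contradict SAP 9.1.2 and the Table 85 note, and would exclude every documented course of up to 10 days that straddles the first dose. For Table 87 this concerns only steroids for non-COVID-19 indications. Table 8 carries a fully unknown stop date, and through 8.3 probably an ongoing drug, to about Day 57 to 63 in a discharged completer. In the example, 9 days become about 58. How much the arm means move depends on the share of fully unknown stops, which the documents do not give: about 2.5 days at 5% and 9.8 days at 20%, if the affected courses resemble the example.

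The effect is confined to descriptive summaries: counts of courses running at dosing, onset, and duration. The primary analysis is untouched, because it adjusts for baseline steroid use and uses none of these derived values. The rules are the same in both blinded arms, so bias between arms is possible but not shown.

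**What to change.** 1. In the footnotes to Tables 86 and 87, replace the definition with that of SAP 9.1.2. Report by arm two separate rows: ongoing at first dose, and newly started after first dose.
2. In Table 8, cap imputed stop dates for these drugs at Day 29. Because the cap still gives 27 days against 9 in the example, also report duration for known stop dates only.
3. Reconcile schedule footnotes 6 and 10 (Protocol 1.2 and the copy in SAP Table 10) with the medication-review row, footnote 12 and Protocol 6.5.1, so that sites know whether steroids and COVID-19 therapies are asked about at telephone contacts to Day 29.
4. Correct the reference to Table 78 in SAP 8.3.

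The cost is small: wording and programming edits to two shells and one imputation rule, and medication items confirmed on calls already made. No new visit or procedure is needed. Items 1, 2 and 4 need only SAP changes and can be made before database lock.

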10.1 Disposition of Subjects

Figure 1: CONSORT Flow Diagram

[Implementation note: Update final CONSORT diagram to include only the two treatment groups applicable to each stage.]

[figure not shown]
[figure not shown]

Figure 2: Adjusted Odds Ratios and 95% Confidence Interval of Inferior Clinical Status Score at Study Visit Day 8 Using a Proportional Odds Model: Overall and for each Subgroup — mITT Population

[Implementation note: The reference group for odds ratio calculation is the placebo group.]

[figure not shown]

Figures with similar format:

- Figure 3:** Adjusted Odds Ratios and 80% Confidence Interval of Inferior Clinical Status Score at Study Visit Day 8 Using a Proportional Odds Model: Overall and for each Subgroup — mITT Population
- Figure 4:** Adjusted Odds Ratios and 95% Confidence Interval of Inferior Clinical Status Score at Study Visit Day 15 Using a Proportional Odds Model: Overall and for each Subgroup — mITT Population
- Figure 5:** Adjusted Odds Ratios and 80% Confidence Interval of Inferior Clinical Status Score at Study Visit Day 15 Using a Proportional Odds Model: Overall and for each Subgroup — mITT Population
- Figure 6:** Adjusted Odds Ratios and 95% Confidence Interval of Inferior Clinical Status Score at Study Visit Day 29 Using a Proportional Odds Model: Overall and for each Subgroup — mITT Population
- Figure 7:** Adjusted Odds Ratios and 80% Confidence Interval of Inferior Clinical Status Score at Study Visit Day 29 Using a Proportional Odds Model: Overall and for each Subgroup — mITT Population

Figure 8: Kaplan-Meier Plot for Time to Sustained Recovery through Day 60 defined by 8-point Ordinal Scale — mITT Population

[Implementation note: For time to sustained recovery, create individual figures 8A through 8F for all subjects, baseline steroid use=Yes, No and baseline ordinals score=5,6,7]

Figures with Similar Format:

[figure not shown]
Figure 9: Kaplan-Meier Plot for Time to Improvement by at least One Category in the Ordinal Scale through Day 60 — mITT Population

Figure 10: Kaplan-Meier Plot for Time to Improvement by at least Two Categories in the Ordinal Scale through Day 60 — mITT Population

[Implementation note: For time to improvement KM figures, create one figure for all subjects in the analysis population.]

Figure 11: Kaplan-Meier Plot for Time to Mechanical Ventilation or Death through Day 29 — mITT Population

[Implementation note: For time to mechanical ventilation or death, create individual figures 11A through 11F for all baseline dexamethasone use=Yes, No and Baseline ordinal score=5,6,7.]

Figures with similar format:

[Implementation note: For the figures below, create only one figure for all subjects in the analysis population.]

Figure 12: Kaplan-Meier Plot for Time to Death through Day 15 — Safety Population

Figure 13: Kaplan-Meier Plot for Time to Death through Day 29 — Safety Population

Figure 14: Kaplan-Meier Plot for Time to Death through Day 60 — Safety Population

Figure 15: Kaplan-Meier Plot for Time to Death, SAE or Grade ≥ 3 TEAEs through Day 60 — Safety Population

Figure 16: Adjusted Hazard Ratios and 95% Confidence Intervals of Time to Sustained Recovery through Study Visit Day 60 Using a Cox Proportional Hazard Model Overall and for each Subgroup — mITT Population

[figure not shown]

Figure with Similar Format:

Figure 17: Adjusted Hazard Ratios and 80% Confidence Interval of Time to Sustained Recovery through Study Visit Day 60 Using a Cox Proportional Hazard Model Overall and for each Subgroup — mITT Population

Figure 18: Distribution of Ordinal Scores by Study Days — mITT Population

[figure not shown]
[figure not shown]

Figure 19: Bee Swarm Plot of Oxygenation Days through Day 29 — mITT Population

[Implementation note: Update colors for treatment groups to match colors used for KM curves.]

[figure not shown]
Figures with similar format:

Figure 20: Bee Swarm Plot of Non-Invasive/High-Flow Oxygen Days through Day 29 — mITT Population

Figure 21: Bee Swarm Plot of Invasive Mechanical Ventilation/ECMO Days through Day 29 — mITT Population

Figure 22: Bee Swarm Plot of Hospitalization Days through Day 29 — mITT Population

Figure 23: Frequency of Non-Serious Related AEs by MedDRA System Organ Class and Severity — Safety Population, All Subjects

[figure not shown]
Figures with similar format:

Figure 24: Frequency of Non-Serious Related AEs by MedDRA System Organ Class and Severity — Safety Population, Actual Baseline Ordinal Score 5

Figure 25: Frequency of Non-Serious Related AEs by MedDRA System Organ Class and Severity — Safety Population, Actual Baseline Ordinal Score 6

Figure 26: Frequency of Non-Serious Related AEs by MedDRA System Organ Class and Severity — Safety Population, Actual Baseline Ordinal Score 7

Figure 27: Incidence of Non-Serious Related AEs by MedDRA System Organ Class and Severity — Safety Population, All Subjects

[figure not shown]
Figures with similar format:

Figure 28: Incidence of Non-Serious Related AEs by MedDRA System Organ Class and Severity — Safety Population, Actual Baseline Ordinal Score 5

Figure 29: Incidence of Non-Serious Related AEs by MedDRA System Organ Class and Severity — Safety Population, Actual Baseline Ordinal Score 6

Figure 30: Incidence of Non-Serious Related AEs by MedDRA System Organ Class and Severity — Safety Population, Actual Baseline Ordinal Score 7

Figure 31: Mean and Standard Deviations of CRP by Study Days — Safety Population

Figures with similar format:

Figure 32: Mean and Standard Deviations of Ferritin by Study Days — Safety Population

Figure 33: Mean and Standard Deviations of D-Dimer by Study Days — Safety Population

Figure 34: Mean and Standard Deviations of Fibrinogen by Study Days — Safety Population

Figure 35: Mean and Standard Deviations of LDH by Study Days — Safety Population

